Parents and youth (Phases 1 and 2) will be recruited through community partners including but not limited to local Arc chapters, the Arc of Massachusetts, the Massachusetts Sibling Support Network (MSSN), Autism/Asperger Network (AANE), and Boston Medical Center. These community partners may distribute a recruitment flier via in-office postings, postal mail, and email, or they may include information about the study on their social media pages. Participants also may be recruited via our Community Advisory Board or word of mouth. Finally, families may be recruited by re-contacting families that either (a) participated in our previous autism-focused studies and provided permission to learn about future studies or (b) who expressed interest in previous studies but were not eligible and asked to learn of future research opportunities.

When recruiting parents and youth for Phase 1, participant characteristics will be reviewed periodically to ensure breadth in the sample based on family race and ethnicity as well as youth age. Continued recruitment will target families with characteristics not as well represented in the sample.

When recruiting families for Phase 2, we will enroll a stratified sample to ensure that families of different races and ethnicities are included, as follows: Black (n = 4-5), Asian (n = 4-5), Latinx of any race (n = 4-5), non-Latinx white (n = 4-5). We will ask about family race/ethnicity during the telephone screen.

Community providers. For Phase 1, community providers will be identified through local and state-wide Arc chapters; recruitment fliers will be posted in the local offices and distributed via email. Additionally, we will use IRB-approved recruitment materials to recruit through social media (e.g., Facebook page). For Phase 2, we will hire 2-4 community-based

providers to serve as program facilitators. These providers also will serve as research participants when providing feedback on the program via session feedback forms and exit interviews.

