Finally, Phase 1 participants who (1) speak English or Spanish and (2) provide consent to be re-contacted for future research opportunities may be contacted about participation in another study. The research team from Protocol #5790E may reach out to ascertain these participants' interest in completing two standardized measures of the skills and abilities of the adolescent/young adult on the autism spectrum. During the consent process for Protocol #5790E, participants will be informed that their questionnaire data will be linked with the qualitative interviews completed as part of this study. For those families who consent to participate in questionnaires as part of Protocol #5790E, their qualitative data from this study will be shared with the Protocol #5790E research team.

Phase 2: Proof-of-Concept Testing.

Once the program is finalized, 20 families will participate in proof-of-concept testing to assess program acceptability and feasibility. This step is crucial due to the plan to utilize community providers to deliver the program in a telehealth format. Given the small scope of the current project, participating families will need to be fluent in English (not necessarily as a first language) to participate in the trial. The sample will be stratified by race/ethnicity, including approximately equal numbers of families who identify as Black, Latinx of any race, Asian, and non-Latinx white. Parent race/ethnicity will be ascertained during the telephone eligibility screener.

Each service provider will receive in-depth training on the principles and components of the program prior to implementation and will participate in weekly meetings to monitor progress, troubleshoot concerns, and receive intensive consultation on the program. Parents will

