By signing this form, you are indicating that you have reviewed the application, that you agree to serve as the Co-PI for this study with the student and that you will be responsible for the ethical conduct of this student's human subjects research.

Faculty Advisor (print name):

Signature:

Date:

IRB School Reviewer, if applicable (print name):

Signature:

Date:

Statistical Analysis Plan

To assess clinically-significant change in treatment targets and outcomes, we will use both anchor-based and distribution-based approaches. Regarding anchor-based approaches, we will assess changes on proposed treatment targets (parent self-efficacy and expectations for adult outcomes) and program outcomes (transition planning activities and attainment of personalized program goals) in relation to self-reported global assessment of change. Global assessments are considered to be sensitive to change and are obtained by asking participants to think back over a specific period of time (i.e., since before participation in Families FORWARD) and indicate the presence and direction of change in their functioning from that time to the present (i.e., improvement, decline, no change). We will use Pearson correlations to assess associations between global assessment ratings and pre/post-program change scores on treatment targets and outcomes. Regarding distribution-based approaches, we will compare pre- to post-program changes in treatment targets and program outcomes to measures of variability within the sample. We will complete these analyses using standard errors of measurement (SEM), standard deviations (SD), and effect sizes (ES). SEM of 1.0, SD of 0.50, and/or ES (Cohen's d) of 0.20 will be indicative of clinically-significant change. We will analyze qualitative exit interview data using applied thematic analysis. Although our sample is not large enough to reach saturation within each racial/ ethnic group, a nuanced analysis according to race/ethnicity is important for our research question that addresses feasibility, acceptability, and perceptions of program benefit across diverse participants. The goal of proof-of-concept testing is not to demonstrate thematic saturation, but rather, to inform the promise of an intervention to guide future work. We will conduct all analyses for the entire sample and again separately for each racial/ethnic group (Black, Latinx, Asian, and non-Latinx white), since outcomes may differ across groups.

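### The only anchor-based statistic is a correlation, which gives no value for meaningful change and cannot show whether observed change reached one

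*Combined protocol and SAP*

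**What the plan says.** The SAP opens with its purpose: "To assess clinically-significant change in treatment targets and outcomes, we will use both anchor-based and distribution-based approaches".

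For the anchor half, participants think back to before the program and "indicate the presence and direction of change in their functioning from that time to the present (i.e., improvement, decline, no change". The rating therefore records whether there was change and in which direction; no grading of its size is described. The analysis is one sentence: "We will use Pearson correlations to assess associations between global assessment ratings and pre/post-program change scores on treatment targets and outcomes".

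The SAP names no mean change by anchor category, no cut-off, no minimum correlation for an acceptable anchor, no numeric coding of the three answers, and no rule for a rating that does not vary. The numeric criteria ("SEM of 1.0, SD of 0.50, and/or ES", the last with a Cohen's d of 0.20) belong to the distribution-based half and are not tied to the anchor.

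On size, Section L (Phase 2) says that "20 families will participate in proof-of-concept testing". Section J sets the strata as "Black (n = 4-5), Asian (n = 4-5), Latinx of any race (n = 4-5), non-Latinx white (n = 4-5". The SAP then adds: "We will conduct all analyses for the entire sample and again separately for each racial/ethnic group". The correlation is therefore also planned in groups of 4 or 5.

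**The concern.** An anchor is used to attach meaning to a scale: how many points go with families saying that things improved, and did the observed change get that far? A correlation addresses a different and prior question, whether the anchor is related to the scale at all. As the SAP stands, that prior check is the whole anchor analysis.

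There is a second, practical problem. Pearson's r needs the ratings to vary. With three possible answers, no comparison group and subgroups of 4 or 5, identical answers within a subgroup are quite possible, and the planned statistic then does not exist.

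At stake is what the proof-of-concept study passes on to later work. Followed as written, the anchor half would yield a set of coefficients, some perhaps missing, and no statement in scale units about change that families notice.

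**Working it through.** The documents give no target correlation, significance level or sample-size derivation for this analysis, so there is no stated figure to reproduce. The check rests on the properties of r and on assumed response shares.

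**Inputs from the documents:** 20 families; four groups of 4–5; three anchor answers. **Assumptions:** the share p answering 'improvement', taken from 0.6 to 0.9; the remainder q = 1 − p split 3:1 between 'no change' and 'decline'; independent answers.

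**1. r carries no information on the size of change.** r = cov(change, rating) / (SD of change × SD of rating). Adding a constant c to every change score alters neither the covariance nor the SD of change, so r is the same.
- Simulated example with 20 families: r = 0.257 before and 0.257 after adding 5 points to everyone.
- Constructed example: ten families change by −1 and answer 'no change'; ten change by −5 and answer 'decline'. Then r = 1.0, while no family improves and the mean change is (10 × −1 + 10 × −5)/20 = −3.

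**2. r is undefined when answers are identical,** because the SD of the rating is 0. The chance of that in a group of n is P = p^n + (0.75q)^n + (0.25q)^n. The chance that it happens in at least one of four groups is 1 − (1 − P)^4. For p = 0.7 and n = 5: P = 0.1681 + 0.0006 + 0.0000 = 0.1686 (from unrounded terms), and 1 − 0.8314^4 = 0.52.

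| Share 'improvement' | One group of 5 | At least one of four groups of 5 | At least one of four groups of 4 | Whole sample of 20 |
|---|---|---|---|---|
| 0.6 | 0.08 | 0.28 | 0.45 | 0.000 |
| 0.7 | 0.17 | 0.52 | 0.67 | 0.001 |
| 0.8 | 0.33 | 0.80 | 0.88 | 0.012 |
| 0.9 | 0.59 | 0.97 | 0.99 | 0.122 |

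Four groups of at most 5 make 20 families only if each has 5. Groups of 4 would apply if fewer families were enrolled or had post-program data.

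**3. Where r can be computed in a subgroup, it is uninformative.** Fisher-z 95% CI: tanh(atanh(r) ± 1.96/√(n − 3)). At an observed r of 0.5 this gives 0.07 to 0.77 with n = 20, −0.68 to 0.96 with n = 5, and −0.89 to 0.99 with n = 4.

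**4. What mean change by category would deliver.** The 95% CI half-width, in units of the SD of change within the category, is t(0.975, k − 1)/√k for k families.
- k = 10: 0.72; k = 16: 0.53; k = 18: 0.50; k = 20: 0.47.
- The interval exists for any category with at least two families, including when all 20 answer alike.
- Comparing categories is much weaker. With 80% 'improvement' and the 3:1 split, about 20 × 0.15 = 3 families answer 'no change'. The chance of 0 or 1 such families is 0.85^20 + 20 × 0.15 × 0.85^19 = 0.039 + 0.137 = 0.18. With 16 improved and 3 unchanged, the half-width of the difference is 2.11 × √(1/16 + 1/3) = 1.3 SD.

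**The case against.** **The rest of the plan covers benefit.** This stands. The distribution-based half compares pre/post change with 0.50 SD and d = 0.20, and exit interviews cover satisfaction and how far the program met participants' needs. A reader might infer that a program helping every family would be reported as having no effect. The documents do not support that: a mean gain of 0.8 SD would pass both thresholds whatever r turned out to be. A low r would say that the rating does not track the scale, not that families failed to benefit.

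**A near-zero r under uniform improvement is easy to construct, but proves little.** If 20 families all gain 4 to 6 points and 18 answer 'improvement' and 2 'no change', r can be 0.00. Ratings in that example are unrelated to change by construction. In a simulation of that kind (mean change 0.8, SD of change 0.5), the improved-minus-unchanged difference is also centred on 0, with a 95% range of about −0.74 to 0.73.

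**No significance rule is breached.** Cutting the anchor to three uneven categories weakens r: an assumed underlying correlation of 0.50 falls to about 0.36 when 80% answer 'improvement'. A reader might set this against 0.444, the two-sided 5% critical value for n = 20. The SAP states no test of r, so that comparison faults it against a rule it does not contain.

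**An undefined r misleads nobody and is mainly a subgroup matter.** Largely true. In the whole sample it is unlikely unless about 90% or more answer 'improvement', and the shares are assumptions. But the SAP does order the subgroup analyses and gives no rule for this case.

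**The item is not fixed.** The three categories rest on one parenthesis in the SAP, and no global-change item appears in the Time 2 measures in Section L, which defers further Phase 2 measures to an amendment. That leaves room to improve the item; it does not supply the missing analysis.

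**Conclusion.** The concern holds in this form: the anchor half is meant to assess clinically significant change, and its only statistic cannot do so. That conclusion is algebraic and needs no assumption. The correlation is legitimate as a check on the anchor; the flaw is that nothing follows it.

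The size of the computability problem depends on the assumed response shares. Across 60–90% 'improvement', the chance of at least one undefined subgroup coefficient runs from 0.28 to 0.97 with groups of 5, against 0.00 to 0.12 in the whole sample.

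The consequence is an anchor result that does not answer its own question, in a 20-family proof-of-concept study with no confirmatory decision resting on it. It is not a false conclusion of no benefit. The change is worth making because it is cheap, not because the study fails without it.

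**What to change.** In the SAP's anchor-based text:

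- For the whole sample and each target and outcome, report the number of families and the mean change with 95% CI in each anchor category.
- Set the mean change among families answering 'improvement' beside that among 'no change' where both have enough families. Present this as description, not as a firm threshold for meaningful change.
- Keep a Spearman correlation, in the whole sample only, as a check that the anchor tracks the measure.
- Within racial/ethnic groups, give counts by anchor category and individual changes in place of r.
- If the global item has not yet been fielded, consider graded response options.

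Cost: a few lines of SAP wording and one descriptive table, with no extra data unless the item is regraded. Downsides: estimates are imprecise (half-width about 0.5 SD with 16–18 families in a category), 'no change' and 'decline' may hold very few families or none, graded options would thin the categories further, and the by-group correlation is given up.

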To assess acceptability, descriptive statistics (mean, median, standard deviation) will be calculated for quantitative acceptability ratings. Exit interview data about program usefulness and value will be evaluated using applied thematic analysis. Analyses will be conducted with the whole sample and separately for each racial/ethnic group. To assess feasibility, we will calculate the number of eligible participants who enrolled in the pilot trial. Retention will be presented descriptively as the average number of sessions completed and follow-up rates within each racial/ethnic group. To assess selective attrition, we will use t-tests and chi squares to evaluate the demographic and autism-related characteristics of families who complete the program vs. those who do not complete the program; these analyses will be conducted for the entire sample. To assess feasibility of the telehealth approach, we will capture technology issues during review of session recordings and will track the number of families who required a tablet to be loaned to them in order to participate in the program.

To assess viability of research procedures and measures, rates of completion for pre- and post-program measures will be described descriptively. We will use t-tests and chi squares to evaluate the demographic and autism characteristics of families who complete the measures vs. those who are lost to follow up; these analyses will be conducted for the entire sample. To assess participant understanding of measures, missing data and inconsistent response patterns will be recorded. Data collection time will be calculated descriptively (mean, standard deviation, range); participant burden regarding completing study measures will be captured qualitatively during exit interviews and will be summarized using applied thematic analysis. Fidelity to the program manual will be assessed by evaluating session recordings against checklists of required components and calculating the percentage of required components present.

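### The clinically significant change thresholds and the Pearson correlations are repeated within racial/ethnic groups of 4-5 families, where sampling error decides the result

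*Combined protocol and SAP*

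**What the plan says.** Section L (Phase 2) states that "20 families will participate in proof-of-concept testing to assess program acceptability and feasibility". Section J stratifies them as "Black (n = 4-5), Asian (n = 4-5), Latinx of any race (n = 4-5), non-Latinx white (n = 4-5".

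The opening paragraph of the Statistical Analysis Plan sets out two ways of judging change.
- Anchor-based: "We will use Pearson correlations to assess associations between global assessment ratings and pre/post-program change scores".
- Distribution-based: "we will compare pre- to post-program changes in treatment targets and program outcomes to measures of variability within the sample". A change of 1.0 SEM counts, and the rule continues: "SD of 0.50, and/or ES (Cohen's d) of 0.20 will be indicative of clinically-significant change".

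The paragraph ends by extending this to the groups: "We will conduct all analyses for the entire sample and again separately for each racial/ethnic group". The reason given is that outcomes may differ between them. In the same paragraph the plan concedes that the sample is too small for thematic saturation within each group. It makes no such statement about the quantitative results, and it plans no confidence intervals for them.

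The next paragraphs of the plan set their own scope. For acceptability: "Analyses will be conducted with the whole sample and separately for each racial/ethnic group". Retention is described within each group. Both sets of t-tests and chi squares, for selective attrition and for loss to follow-up, are restricted: "these analyses will be conducted for the entire sample". Completion rates, data collection time and fidelity carry no by-group instruction there.

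**The concern.** A threshold verdict turns a noisy estimate into a yes or no. Applied to the mean of 4 or 5 families, four such verdicts will usually conflict by chance. The plan's stated reason for the group analyses is to see whether outcomes differ, so conflicting verdicts are the result a reader will look for and interpret.

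The stakes are practical. The project is motivated by racial and ethnic disparities in service use, and the proof-of-concept results are meant to guide later work. A chance finding that the program produced clinically significant change in some groups and not in others could misdirect the next stage.

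**Working it through.** The plan gives no alpha, power or precision calculation, so there is no figure of its own to reproduce.

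**Inputs from the documents:** four groups of n = 4-5 (Section J); thresholds of 0.50 SD and d = 0.20 (Statistical Analysis Plan).

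**Assumptions, not in the documents:** normal scores; pre/post correlation rho of 0.5 or 0.7; equal SDs before and after; no dropout; true change of 0 or 0.3 baseline SD, the same in every group.

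**1. Precision of a group's mean change.** In baseline-SD units, the SD of change is sqrt(2(1 - rho)): 1.00 at rho = 0.5 and 0.775 at rho = 0.7. Treating the baseline SD as known, the 95% half-width is t x SD of change / sqrt(n).
- n = 5: 2.776 x 1.00 / 2.236 = 1.24, and 2.776 x 0.775 / 2.236 = 0.96.
- n = 4, rho = 0.5: 3.182 x 1.00 / 2 = 1.59.

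The thresholds to be judged are 0.20 and 0.50.

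**2. Chance that the d >= 0.20 verdict misleads, n = 5, one common known SD.** The standard error is 1.00/2.236 = 0.447 or 0.775/2.236 = 0.346.
- No true change: one group passes with probability 1 - Phi(0.20/0.447) = 0.327, or 1 - Phi(0.20/0.346) = 0.282. At least one of four passes: 1 - 0.673^4 = 0.795, or 1 - 0.718^4 = 0.734.
- True change of 0.3 SD everywhere: one group passes with probability p = Phi(0.10/0.447) = 0.588, or Phi(0.10/0.346) = 0.614. The groups disagree with probability 1 - p^4 - (1 - p)^4 = 0.851, or 0.836.

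**3. The same with the SD estimated (100,000 simulated trials, four groups of 5).**

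| Quantity | Scaling SD | rho = 0.5 | rho = 0.7 |
|---|---|---|---|
| Groups disagree, true change 0.3 SD in all | own group | 85% | 83% |
| | whole sample | 85% | 83% |
| At least one group passes, no true change | own group | 81% | 76% |
| | whole sample | 80% | 74% |

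These rates are per outcome; the plan names four targets and outcomes. With 4 per group and own-group scaling, the no-change figures are 83% and 79%.

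**4. The 0.50 SD threshold, no true change, n = 4 or 5, rho from 0.5 to 0.8.** At least one group passes in 27-58% of trials with own-group SDs and in 17-51% with one pooled within-group SD.

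**5. Correlations.** Fisher's z for r = 0.5 is 0.549, with standard error 1/sqrt(n - 3).
- n = 5: 0.549 +/- 1.96 x 0.707 runs from -0.837 to 1.935, so r lies between -0.68 and 0.96.
- n = 4: 0.549 +/- 1.96 x 1 gives r between -0.89 and 0.99.

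**6. Stability of a group's SD.** The chi-square 95% CI runs from 0.60 to 2.87 times the estimate at n = 5 and from 0.57 to 3.73 times at n = 4. With equal true SDs, the largest of four group SDs has a median of 2.13 times the smallest at n = 5.

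**The case against.** The best defence is that this is a proof-of-concept study of acceptability and feasibility. Describing results by group is a deliberate aim, no between-group test is planned, and the thresholds are worded as indicative and joined by and/or. That stands as a reason to keep by-group description. It does not justify attaching threshold verdicts to each group, which the plan does without any limit on how the numbers are read.

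Four stronger readings are tempting, and the documents do not support them.

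- A reader might infer that every quantitative analysis is repeated by group. The plan keeps the attrition and loss-to-follow-up tests at whole-sample level, and gives no by-group instruction for completion rates, data collection time or fidelity in the paragraphs that define them.
- A reader might infer that each group is judged against its own SD and that this causes the problem. Own-group scaling is a natural reading of running the analyses separately, but the plan refers only to variability within the sample. It is an ambiguity to settle. Steps 2 and 3 show that it does not drive the d >= 0.20 result, although a common SD helps somewhat at the 0.50 threshold.
- A reader might judge the correlations by the size needed for significance in 4 or 5 families. The plan states no alpha or significance rule for them; the interval width is the relevant measure.
- A reader might conclude that no group difference could ever show. For illustration, a two-sided 0.05 comparison of two such groups has 9-11% power for a difference of 0.5 SD of change, but 66-79% for 2 SD. Very large differences could emerge.

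**Conclusion.** The point holds for the clinically significant change analyses: the by-group threshold verdicts and the by-group Pearson correlations. In groups of 4-5 families these are dominated by sampling error for small and moderate effects, and conflicting verdicts are the usual outcome when the true effect is identical.

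The exact percentages depend on the assumed correlation and true change, and on taking the d >= 0.20 criterion alone. They show what is likely, and do not establish that this trial will report a false group difference. The conclusion is not sensitive to which SD is used, and any dropout would make the groups smaller still. Which SD scales by-group change remains unspecified and should be stated in any case.

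**What to change.** Amend the Statistical Analysis Plan as follows.

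1. Apply the SEM, SD and d thresholds and the Pearson correlations to the whole sample only.
2. Present change by group as individual pre/post values and mean change with 95% CI, scaled by the whole-sample baseline SD.
3. State that by-group contrasts in change are descriptive only.
4. Keep thematic analysis, acceptability and retention by group as planned.

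The cost is a change of wording and less analysis than now planned, with no new families, data or measures. The loss is group-specific verdicts, which 4-5 families per group could not support. Changing only the SD would not be enough, because most of the noise lies in the group means.

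### In 20 families, t-tests and chi-squares will probably miss moderate selective attrition, and the chi-square p-values are unreliable

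*Combined protocol and SAP*

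**What the plan says.** The feasibility part of the Statistical Analysis Plan reads: "To assess selective attrition, we will use t-tests and chi squares to evaluate the demographic and autism-related characteristics of families who complete the program", with families who do not complete the program as the comparison group. The following paragraph, on viability of research procedures and measures, applies t-tests and chi-squares again to "families who complete the measures vs. those who are lost to follow up". For both it adds that "these analyses will be conducted for the entire sample".

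The sample size is in Section L, Phase 2: "Once the program is finalized, 20 families will participate in proof-of-concept testing to assess program acceptability and feasibility". Section J divides these families into four racial/ethnic strata of 4 to 5 each. The baseline characteristics available for comparison are in the Section L measures list: a demographics form, the SCQ (autism symptoms) and the W-ADL (functional independence).

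The plan also provides a description without tests: "Retention will be presented descriptively as the average number of sessions completed and follow-up rates within each racial/ethnic group".

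For the attrition comparisons, the documents give no expected attrition rate, significance level, exact-test alternative for sparse tables, effect size or interval, or rule for reading a non-significant result.

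**The concern.** The smaller group in each comparison will be the families who drop out, and in a sample of 20 that is likely to be a handful. Two separate problems follow.

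- **Power.** A t-test of a few families against the rest can pick up only very large differences. A family type that leaves the program more often could go unflagged.
- **Validity.** The chi-square p-value rests on a large-sample approximation that these cell counts do not support. Its real false-positive rate depends on how many families happen to have the trait and how many happen to drop out.

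Phase 2 exists to assess acceptability and feasibility, so who stays and who leaves is one of its useful products. The method chosen should show how much, or how little, 20 families can say about it.

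**Working it through.** **Inputs.** From the documents: N = 20 families and four strata (taken as 5 each). Assumed, because the documents give no figure: k = 2 to 6 dropouts (10% to 30%), two-sided alpha 0.05, 80% power. The plan states no power or detectable difference for these tests, so there is no figure to reproduce.

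**t-test.** With k dropouts and 20 − k completers, the standard error of a standardized difference is SE = √(1/k + 1/(20 − k)), on 18 degrees of freedom with critical value 2.101. For 80% power the noncentrality d/SE must be 2.963, so the detectable difference is d = 2.963 × SE. The approximate 95% interval half-width is 2.101 × SE.

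| Dropouts | SE | Detectable d (80% power) | Power at 0.8 SD | Power at 1.5 SD | Half-width |
|---|---|---|---|---|---|
| 2 | 0.745 | 2.21 | 17% | 48% | 1.57 |
| 3 | 0.626 | 1.86 | 23% | 62% | 1.32 |
| 4 | 0.559 | 1.66 | 27% | 72% | 1.17 |
| 5 | 0.516 | 1.53 | 31% | 78% | 1.08 |
| 6 | 0.488 | 1.45 | 34% | 83% | 1.03 |

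The assumptions do not drive the result. At alpha 0.10 the detectable difference still runs from 1.93 to 1.26 SD. With 16 families (four strata of 4) it runs from 2.28 to 1.56 SD. Even a 10/10 split of 20 families needs 1.32 SD.

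**Chi-square, expected counts.** In a 2x2 table whose rarer trait category has m ≤ 10 families, the smallest expected count is at most k × m/20 ≤ k/2. That is below 5 whenever k is below 10. For race/ethnicity, the expected dropouts per group are k/4, or 0.5 to 1.5.

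**Chi-square, true size in 2x2 tables.** With both margins fixed and dropout unrelated to the trait, the count of dropouts with the trait is hypergeometric, so the size can be enumerated exactly. Two neighbouring cases for a trait held by 10 of 20 families show the instability (Pearson, no continuity correction, critical value 3.84):

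- 4 dropouts, all on one side: χ² = 20 × (4 × 10 − 0 × 6)² / (4 × 16 × 10 × 10) = 5.00, which rejects. Its probability by chance is 2 × 210/4845 = 8.7%. No other table rejects, so the true size is 8.7%.
- 3 dropouts, all on one side: χ² = 20 × (3 × 10 − 0 × 7)² / (3 × 17 × 10 × 10) = 3.53, which does not reject. This is the most extreme table, so the true size is 0%.

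Over all 9 × 5 = 45 tables with the trait held by 2 to 10 families and 2 to 6 dropouts, the size exceeds 5% in 16. Leaving aside one corner table (discussed with the objections), the maximum is 11.1%. Fisher's exact test stays at or below 5% in all 45.

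**Chi-square, race/ethnicity by completion (4x2, 5 per group).** With 6 dropouts, χ² = Σ(x − 1.5)² × (1/1.5 + 1/3.5) = 0.952 × Σ(x − 1.5)², critical value 7.81. The patterns that reject are:

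| Dropouts by group | Σ(x − 1.5)² | χ² | Ways |
|---|---|---|---|
| 5,1,0,0 | 17 | 16.19 | 60 |
| 4,2,0,0 | 11 | 10.48 | 600 |
| 3,3,0,0 | 9 | 8.57 | 600 |
| 4,1,1,0 | 9 | 8.57 | 1500 |

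The size is 2760/38760 = 7.1%. The Freeman-Halton test drops the last pattern, giving 1260/38760 = 3.3%. For 2, 3, 4 and 5 dropouts the chi-square size is 0%, 3.5%, 0.4% and 2.0%.

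**What an exact test does not do.** For dropout of 10% versus 40% in two categories of 10 families, power is 29% with uncorrected Pearson and 15% with Fisher.

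**The case against.** The strongest reply is that this is a secondary feasibility check in a 20-family proof-of-concept study, with no decision tied to it, and that no test rescues 20 families. That stands, and it sets the severity. The descriptive reporting of sessions completed and follow-up by racial/ethnic group also stands: for the study's key stratifier the reader will see the pattern without a p-value. It does not cover autism severity, functional independence, age or income, for which only the tests are planned.

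Several stronger readings are tempting, and the documents or the arithmetic do not support them.

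- **That real selective dropout is certain to be missed.** Power at 1.5 SD is 48% to 83%, so large differences have a fair chance of being found.
- **That a null result will be taken as no selective attrition, or that this check underwrites the pre/post results.** The plan says neither. It places the comparisons under feasibility and viability of procedures.
- **That the chi-square size runs as high as 19.5%.** That value belongs to one corner table (exactly 2 families with the trait and exactly 2 dropouts). The mean over the 45 tables is 4.4%. With Yates correction, on which the plan is silent, the maximum is 3.3%.
- **That two dropouts from one racial/ethnic group expose a chi-square defect.** Chi-square gives 6.67 (p = 0.083), but Freeman-Halton gives 40/190 = 0.21. Two events simply carry little information.
- **That a chance finding has probability 0.71.** This is 1 − 0.95^24, for 24 independent tests each at exactly 5%. The plan fixes no number of characteristics, the two comparisons probably share many families, and the tests do not run at 5%.

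**Conclusion.** The concern holds as a minor point of method. Under the assumed 2 to 6 dropouts, alpha 0.05 and 80% power, the t-tests detect only differences of 2.21 down to 1.45 SD, so moderate selective dropout will probably, not certainly, be missed. The low power persists for any dropout count up to an even split.

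The chi-square approximation is unreliable at these counts and can err in either direction. How far it exceeds 5% depends on the continuity correction being omitted. The sparse expected counts do not depend on that choice.

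Nothing in the documents shows that the team will misread a non-significant result. The gap is that the plan neither rules that reading out nor reports the size and uncertainty of the differences.

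**What to change.** In both places in the Statistical Analysis Plan:

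1. Report the characteristics of completers and non-completers descriptively. For continuous characteristics such as SCQ, W-ADL and youth age, make standardized differences with 95% confidence intervals the main result.
2. If p-values are kept for categorical characteristics, replace chi-square with Fisher's exact test (Freeman-Halton for more than two categories).
3. State that a non-significant result will not be interpreted as absence of selective attrition.

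This changes wording only, with no added data or visits. The intervals will be visibly wide (half-width about 1.0 to 1.6 SD), which is an honest picture of what 20 families can show.
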